Between December 2020 and January 2021, 75 PSH tenants were referred to the research team. Fifteen PSH tenants declined to participate, resulting in 60 individuals who answered a survey-administered baseline assessment and were randomized into the intervention or waitlist control group. The CAPABLE team then received the list of 30 tenants randomized to initially receive the intervention. Two tenants decided they no longer wanted to participate in the program and one could not be recontacted (the team later discovered this person had died), leaving 27 who received the intervention starting in February 2021. In June 2021, the 30 tenants in the waitlist control group completed a follow-up research assessment, along with the 17 who had finished the CAPABLE intervention at that time. By September 2021, the remaining 10 tenants all completed the CAPABLE program but only nine had completed the follow-up research assessment; one person declined to complete but was contacted 6 months later and completed the follow-up assessment at that time.

Most intervention visits occurred in person at the participant's residence (a few visits by the nurse were conducted by phone if the tenant was able to share progress and could follow guidance through this format). All research data collection was conducted by telephone as part of COVID-19 safety protocols. PSH tenants received a \$20 gift card for completing the baseline assessment and a \$25 gift card for completing the follow-up assessment.

All data were collected and managed using the REDCap platform. Measures collected only at baseline included demographic characteristics, years in current PSH unit, and cumulative years spent homeless. Tenants were also asked about history and number of falls, emergency room visits, and overnight hospitalizations within the last year at baseline; these items were asked again at follow-up but used only a 6-month retrospective. Additional health-related outcomes measured at baseline and follow-up included information on: ADLs and IADLs; falls efficacy; depression; pain interference with usual activities; self-rated health; and overall quality of life. A description of primary outcome measures are included in the following table:

Table 1. Description of primary outcome measures.

Measure	Description

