Katz Activities of Daily Living Scale	The modified Katz ADL Scale was used to rate ability to bathe, dress, transfer, toilet, and eat using three categories: no difficulty, a little or some difficulty, or a lot of difficulty or inability to perform. ³⁶
The Brief Instrumental Functioning Scale	The Brief Instrumental Functioning Scale was used to assess ability to perform six IADLs on a scale similar to the Katz ADL Scale. ³⁷

Falls	History of falls during the past year was assessed by asking: “Did you fall to the ground in the past year?” ³⁸ The number of falls in the past year was also assessed.
Falls efficacy	Participants rated their confidence they could do each of 10 activities without falling on a 10-point scale, with total scores ranging from 10 (not very confident) to 100 (very confident) using the Tinetti Falls Efficacy Scale.
Depression	Eight of the nine items in the Patient Health Questionnaire-9 were used to measure depression, rated on a 4-point scale of how frequently participants were bothered by the eight problems during a 2-week period (0 = not at all, 1 = several days, 2 = more than half the days, and 3 = nearly every day). ³⁹ Items were summed to obtain a score with minimum and maximum values of 0 to 24, respectively, whereby higher scores represent greater depressive symptoms.
Pain interference with usual activities	Pain interference with usual activities was assessed using an item from the 3-item PEG to assess average pain intensity (P), interference with enjoyment of life (E), and interference with general activity (G) on a 10-point Likert scale from 0 (does not interfere) to 10 (completely interferes).

Statistical Analysis Plan. We conducted a power analysis using G*Power to estimate the power obtained with 100 individuals proposed for this pilot. When specifying an effect size of .30 and a correlation among repeated measures of .70, 70 participants across two groups were needed to achieve an exact power of .80. This allowed our study to have up to a 30% overall dropout rate while maintaining sufficient power.

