The balance between the intervention and control groups at baseline was assessed using Fisher’s exact test for nominal variables, the Cochran–Mantel–Haenszel test for ordinal variables, and two-sample *t*-tests for continuous and count variables. Given that the main analytic goal of this pilot study was to consider the effect size of the intervention, we calculated within- and between-group standardized mean differences (Cohen’s *d*) between time points. These tests were also used to compare differences in falls, ER visits, and hospitalizations between the groups at follow-up. To consider statistically significant changes in key outcomes in each study group (i.e., intervention versus control) between baseline and follow-up, we also used paired *t*-tests. Between-group analyses included a two-sample *t*-test to test whether the mean change in outcomes between baseline and follow-up differed between the intervention and control groups.

Aim 2: Determine what adaptations, if any, need to be made to implement CAPABLE in PSH.

Adaptation of CAPABLE. Following the DAP implementation approach, which was designed to allow an evidence-based practice to be adapted in a planned and considered, rather than ad hoc, manner,⁴⁰ our investigative team monitored the implementation of CAPABLE and worked in conjunction with program leaders, clinicians, clients, county health systems, and model developers to make any adaptations to the model that would also preserve fidelity to core components. For example, we expected that within PSH, CAPABLE would need to include

collaboration with existing PSH case workers and social workers. DAP is a continuously iterative process, in that ongoing experience can inform continued adaptation as needed. Although DAP can be used during all four phases of the implementation conceptual model known as EPIS (i.e., exploration, preparation, implementation, and sustainment),^{41,42} this study focused on two of the phases: preparation and implementation. The initial exploration phase was completed as part of our previous work (see Preliminary Studies section), and the implementation phase represents this next step.

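### The follow-up comparison of falls, a listed primary outcome measure, leaves out the baseline fall data already collected, at a cost in precision of unknown size

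*Combined protocol and SAP*

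**What the plan says.** The analysis paragraph under Aim 1 first lists tests for baseline balance: Fisher's exact for nominal items, Cochran–Mantel–Haenszel for ordinal items, and "two-sample *t*-tests for continuous and count variables". A sentence on Cohen's d follows, and then: "These tests were also used to compare differences in falls, ER visits, and hospitalizations between the groups at follow-up". No covariate and no count model is named anywhere in the plan.

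The baseline information exists. Under Participant recruitment and data collection: "Tenants were also asked about history and number of falls, emergency room visits, and overnight hospitalizations within the last year at baseline". The recall window then changes: "these items were asked again at follow-up but used only a 6-month retrospective".

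Falls appears in the table headed "Table 1. Description of primary outcome measures", as a yes/no item and as a count: "The number of falls in the past year was also assessed". ER visits and hospitalizations are not in that table.

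A later sentence plans a two-sample t-test "to test whether the mean change in outcomes between baseline and follow-up differed between the intervention and control groups". That analysis uses baseline, but the plan does not say whether it covers falls.

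**The concern.** If a tenant's fall rate is partly a stable personal trait, the baseline count predicts the follow-up count. A comparison of follow-up counts alone leaves that predictable variation in the error term. The result is a wider interval and lower power on a primary outcome measure, in a study that analysed 57 tenants when its own power calculation asked for 70.

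The unequal windows are a good reason not to analyse a raw change in falls, since 12-month and 6-month counts are not on the same scale. They are no reason to ignore baseline. A covariate need not share the outcome's window, because the regression coefficient absorbs the difference in scale.

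The stated main goal is to look at effect size, so precision is what the pilot most needs. A rate ratio with an interval would also help in planning a later trial more than a standardized mean difference on skewed counts.

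**Working it through.** **The plan's own figure.** The power calculation gives 70 participants for power .80 with effect size .30 and correlation .70. Reading .30 as Cohen's f, with two-sided alpha .05 (both assumptions), and using a between-groups repeated-measures F test with λ = f²·N·m / (1 + (m − 1)ρ) and df 1 and N − 2:

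- m = 4 measures: N = 70 (power .8025).
- m = 2, the number of assessments in this trial: N = 78 (power at 70 is .765).

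So 70 can be reproduced, but not with two assessments. The 30% dropout allowance matches: 70 / (1 − .30) = 100. The calculation is not specific to falls, and its .70 is the only correlation in the documents.

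**Inputs for falls.** Intervention follow-up: 17 + 9 + 1 late = 27. Control follow-up: 30. Total: 57. Share falling in 12 months: 56%, from the preliminary study (adults aged 45 or older). The baseline to follow-up correlation and the true effect are not given, so both are varied.

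**Approximation.** Adjusting for baseline multiplies the residual variance by (1 − ρ²). Effective N = 57 / (1 − ρ²). The standardized difference detectable with 80% power is 2.8 × √[(1 − ρ²)(1/27 + 1/30)]; unadjusted, 2.8 × .2653 = .743.

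| ρ | Effective N | Detectable difference (SD) | Power at d = 0.6 |
|---|---|---|---|
| unadjusted | 57 | .74 | 60% |
| .3 | 63 | .71 | 64% |
| .5 | 76 | .64 | 73% |
| .7 | 112 | .53 | 88% |

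At ρ = .1 the power gain is under 1 point.

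**Simulated fall counts.** Each tenant has a gamma-distributed fall rate with mean 1. Counts are Poisson. The annual mean μ is set so that P(no fall in 12 months) = .44; for shape 1, 1/(1 + μ) = .44 gives μ = 1.273. The follow-up mean is μ/2. Some settings add period-to-period noise (gamma, shape 2). Power at an assumed rate ratio of .40:

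| Between-tenant rates | t-test | Quasi-Poisson, no baseline | Quasi-Poisson + log(baseline + 0.5) | t-test → baseline-adjusted permutation test (separate runs) |
|---|---|---|---|---|
| shape .6, stable | .364 | .371 | .563 | .38 → .56 |
| shape .6, noise | .264 | .266 | .382 | .30 → .37 |
| shape 1.0, stable | .382 | .353 | .428 | .40 → .47 |
| shape 1.0, noise | .294 | .280 | .332 | .29 → .33 |

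- **Source of the gain.** The count model without baseline does no better than the t-test, so the gain comes from the covariate.
- **Size-controlled gain.** With the permutation test the gains are .18, .07, .07 and .04. At rate ratio .60 they are about .02 to .08.
- **Low end.** With dispersion 1, correlation about .27 and rate ratio .50, power was .271 (t-test), .272 (linear ANCOVA) and .275 (adjusted quasi-Poisson).
- **High end.** With dispersion 2, correlation about .71 and rate ratio .50, it was .232, .415 and .468. The quasi-Poisson gain of .24 comes with a null rejection rate of .066. ANCOVA, at .044 under the null, gains .18.
- **Type I error.** In these two sets of runs the t-test rejected .041 to .052 under the null and the model-based adjusted test .041 to .066 (.075 in one further setting run separately). The adjusted permutation test rejected .049 to .054.

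**The case against.** **The planned test is valid.** A reader might infer that the follow-up comparison is biased because it ignores fall history. The documents do not support that. Tenants were randomized, the t-test holds its type I error, and the plan assesses baseline balance, so an imbalance would at least be visible. This objection stands in full: the point is about efficiency.

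**The large gain is a best case.** It needs highly variable, stable personal fall rates and an assumed rate ratio of .40, and none of this is in the documents. At a rate ratio of .60 or .70 both analyses are badly underpowered with 57 tenants. This stands too, so the gain can only be given as a range.

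**Part of the apparent gain is a liberal test.** This is partly right for the model-based p-value. The permutation test answers it: it holds its size and keeps gains of .04 to .18 at rate ratio .40.

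**The count model is a preference.** Largely so. Linear ANCOVA did nearly as well in most settings. The case for the log link is that it yields a rate ratio.

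**The wording is unclear.** The quoted sentence follows the one on Cohen's d, so the tests it refers to are a matter of inference, and a yes/no fall item would go to Fisher's exact test. Each of these readings is unadjusted. If the later change-score sentence was meant to cover falls, baseline would be used, but by subtracting counts over unequal windows.

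**The scope is falls.** A reader might extend the primary-outcome argument to ER visits and hospitalizations. They are not in Table 1, the documents give no rates for them, and no gain has been computed.

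**Conclusion.** The point holds as a cheap gain in precision for falls. The plan compares falls at follow-up without using a baseline fall history and count that it already has. The planned comparison remains valid, and nothing here shows it to be biased.

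The size cannot be fixed from the documents. With 27 versus 30 tenants the power gain runs from about zero, at a correlation near .3 or with a modest effect, to about .20 under stable, highly variable rates and an assumed rate ratio of .40. The range rests on a gamma-Poisson model, the preliminary study's 56%, and assumed correlations and effects. It would be wrong to read the upper end as the expected gain, or to conclude that adjustment makes the pilot adequately powered for falls. Replacing the t-test by a count model without the baseline covariate would gain essentially nothing.

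**What to change.** 1. **Number of falls.** Compare 6-month counts between arms with the baseline count as a covariate, for example quasi-Poisson or negative binomial with arm and log(baseline count + 0.5). Report the rate ratio with 95% CI.
2. **P-value.** Take it from a permutation test that uses the same adjustment, because the model-based test can be slightly liberal at this sample size (about .06).
3. **Any fall.** Use logistic regression with baseline fall history as the covariate.
4. **Windows.** Do not difference the 12-month and 6-month counts. State that the change-score t-test does not apply to falls, and name the tests that the follow-up sentence refers to.
5. **Reporting.** Data collection is complete, so keep the planned comparison, place the adjusted analysis beside it, and label it as added.
6. **ER visits and hospitalizations.** The same adjustment can be applied as an option, without claiming a known gain.

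The cost is a short passage in the analysis plan and a few lines of code, with no new data. The downside is a modest model assumption, which the permutation p-value largely covers.

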Implementation of CAPABLE. We trained two registered nurses (RNs) and an OT to handle a caseload of 50 PSH tenants. In most cases, the OT made six visits, the RN made four visits, and a handyman made one to two visits to modify the client's home during a 6-month period. However, the program can be completed in fewer visits, with a minimum of four OT visits and three RN visits. CAPABLE home visits are key to meeting participants "where they are." The first visits for the OT and RN were usually 90 minutes each, and the later ones are usually an hour each. Visits are spaced to enable older adults to practice new strategies learned in the previous visit. Visits were allowed to be rescheduled given unforeseen circumstances. There was a clear conclusion or graduation, with the older adult understanding how to use their new

skills and apply them to future situations.¹⁰ For this study, we planned to recruit 100 eligible SRHT tenants. As a result, a waitlist control design was used, for a case-crossover between- and within-subject comparison of the CAPABLE intervention effect.

Participant recruitment and data collection. Starting in December 2020, the PSH support staff began identifying eligible participants for the CAPABLE program. PSH tenants were eligible for the study if they were over the age of 50, had some or a lot of difficulty performing ADLs, and were cognitively intact or had only mild cognitive impairment. Tenants who were perceived to meet these criteria received details about the CAPABLE program from the trained OT, who also asked whether tenants would be interested in participating in a study. Interested tenants were referred to the research team to be screened to confirm eligibility status, obtain informed consent, and randomly assigned to either the intervention or waitlist control group using a random number generator.

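### Scale outcomes are compared by unadjusted change scores; adding a baseline-adjusted ANCOVA would cut the variance by about 13% (plan's correlation of .70, equal SDs assumed) at almost no cost

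*Combined protocol and SAP*

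**What the plan says.** The Statistical Analysis Plan under Aim 1 lists baseline balance tests, Cohen's d within and between groups, paired t-tests within each arm and, between arms, a two-sample t-test "to test whether the mean change in outcomes between baseline and follow-up differed between the intervention and control groups". It contains no ANCOVA, regression or other baseline-adjusted comparison. The same section says that "the main analytic goal of this pilot study was to consider the effect size of the intervention".

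What ANCOVA needs is already in place. Under Participant recruitment and data collection, tenants were "randomly assigned to either the intervention or waitlist control group using a random number generator". The same part says: "Additional health-related outcomes measured at baseline and follow-up included information on: ADLs and IADLs; falls efficacy; depression". That list continues with pain interference, self-rated health and quality of life. The power paragraph assumes "a correlation among repeated measures of .70".

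Falls, emergency visits and hospitalisations are handled differently. The baseline questions cover a year, and "these items were asked again at follow-up but used only a 6-month retrospective". The plan compares these outcomes between groups at follow-up, so this point does not concern them.

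**The concern.** A change score uses the baseline, but it forces the baseline slope to be 1. When the true slope is below 1, subtracting the whole baseline over-corrects. At a slope of .70, 30% of any chance baseline difference between the arms stays in the estimated effect with its sign reversed. On average over randomisations this cancels, so the test is unbiased with correct type I error. In any one trial it adds noise that ANCOVA would remove.

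That noise matters because effect-size estimation is the plan's stated main goal and only about 57 people contribute to each comparison. The interval around each effect is wide, and baseline scores already collected could narrow it. The plan also tests baseline balance but provides no adjusted analysis should an imbalance appear.

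**Working it through.** **The plan's own figure.** The power paragraph says "70 participants across two groups were needed to achieve an exact power of .80" when "specifying an effect size of .30" with correlation .70. Taking .30 as Cohen's f in a repeated-measures between-factors F test (alpha .05, two groups), the noncentrality is f²·N·m/(1+(m−1)ρ) for m measurements. Four measurements give N = 70 (power .8025), three give 72, and the two assessments described give 78 (power .765 at N = 70). So 70 can be reproduced, but not with two assessments. That is a separate matter. The check below takes only ρ from this paragraph, and the effect size only for illustrative power.

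**Inputs.**
- ρ = .70, from the power paragraph.
- 27 intervention participants with follow-up (17 + 9 + 1 late) and 30 controls, from Participant recruitment and data collection.
- SDs at baseline and follow-up: not given. Assumed equal, then varied.

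**Variances**, in units of SD², with k = 1/27 + 1/30 = .0704:
- Change score: 2(1−ρ)k = .60 × .0704 = .0422, so SE = .2055 SD.
- ANCOVA: (1−ρ²)k × [1 + 1/(57−4)] = .51 × .0704 × 1.0189 = .0366, so SE = .1912 SD. The factor 1.0189 is the price of estimating the slope.
- Ratio: .60/.51 = 1.176 in large samples; 1.176/1.0189 = 1.155 here. The reduction is 1 − 1/1.155 = 13.4%.
- Equivalent sample: 57 × 1.155 = 65.8, or about nine more people.
- 95% half-width (t on 55 and 54 df): .412 and .383 SD, about 7% narrower.

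A simulation of 200,000 trials also gave 13.4%. In a further 100,000 trials per effect size, type I error was .049 for both methods and both were unbiased. Counting 26 v 30 (late assessment excluded) gives 13.4%; 30 v 30 gives 13.5%.

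**Illustrative power**, two-sided .05, 27 v 30. The plan does not say whether .30 is d or f. For two groups d = 2f, so f = .30 means d = .60.
- d = .30: .300 (change) and .338 (ANCOVA).
- d = .60: .818 and .869.

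**Sensitivity.** With s = follow-up SD / baseline SD, the large-sample ratio is (1 + s² − 2ρs) / [s²(1 − ρ²)], divided by 1.0189 at 27 v 30.

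| ρ | s | Large-sample ratio | Ratio at 27 v 30 | Variance reduction |
|---|---|---|---|---|
| .70 | 1.0 | 1.176 | 1.155 | 13.4% |
| .50 | 1.0 | 1.333 | 1.309 | 23.6% |
| .90 | 1.0 | 1.053 | 1.033 | 3.2% |
| .70 | 0.9 | 1.331 | 1.307 | 23.5% |
| .70 | 1.1 | 1.086 | 1.066 | 6.2% |
| .70 | 1.2 | 1.035 | 1.016 | 1.6% |
| .70 | 1.43 | 1.000 | .981 | −1.9% |

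The last row is the worst case for ANCOVA: the true slope is 1 (.70 × 1.43), and estimating it costs 1/53 of the variance.

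**The same loss seen as imbalance.** A one-SE baseline difference is √k = .265 SD, which moves the change-score estimate by .30 × .265 = .08 SD. Squared, (.30√k)² = .0063 = (.60 − .51)k. This is the variance difference above, not a second problem.

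**The case against.** The strongest reply is that nothing here is an error. The specified test is valid, and it suits a plan built on pre–post change, because the between-arm difference equals the difference of the two within-arm changes. The gain is modest: .03 SD off the half-width, with power at d = .30 going from .300 to .338. All of that stands, and it is why this is an improvement rather than a fault to be corrected.

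The 13% also rests on one generic planning correlation applied to seven outcomes. The assumption is weakest for ADLs, because eligibility required ADL difficulty and so may narrow the baseline spread. As an illustration, assume bivariate normal scores, ρ = .70 before selection, and entry limited to the most impaired 42% (the ADL prevalence in Preliminary Studies). The baseline variance falls to .322 of its original value, the change variance factor is .09 × .322 + .51 = .539, and ANCOVA's is .51 × 1.0189 = .520. The reduction is then 1 − .520/.539, about 4%. This caveat stands; it lies within the range tabulated above.

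An analysis added after data collection also creates a second set of estimates and room for selection. That is a real cost unless all outcomes are reported and the specified test keeps its standing.

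Finally, three intervention participants and no controls lack follow-up, and 10 of the 27 were assessed after the June 2021 control assessment. These could matter more than the precision gain, but they affect both estimators alike and are separate points.

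**Conclusion.** The concern holds. The plan's only between-arm test of the scale outcomes is an unadjusted comparison of change, although randomisation and matching baseline scores make ANCOVA available for one degree of freedom. At ρ = .70, equal SDs and 27 v 30, the variance falls by 13.4%. Over the SD ratios and correlations tabulated, the result runs from a reduction of about 24% to a loss of about 2%, with ADLs likely towards the smaller gains. The specified t-test remains valid; the case for change is efficiency in a small trial whose stated goal is effect-size estimation.

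**What to change.** For each scale outcome, regress the follow-up score on arm and that outcome's own baseline score. Report the adjusted difference with its 95% CI, standardised by the pooled baseline SD, beside the change-score t-test, which stays as specified. For ADLs, give the difference in raw units as well, since a baseline SD narrowed by eligibility would inflate the standardised effect.

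Because data collection is complete, label this as an added baseline-adjusted analysis and report it for all scale outcomes, not a selection. Do not apply it to falls, emergency visits or hospitalisations, whose recall windows differ between assessments.

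The cost is one regression and one degree of freedom per outcome, plus a labelling sentence. No new data are needed.
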